6.8.2 Permitted Concomitant Medications

The site physician may prescribe necessary and appropriate medications in accordance with local country regulations during the study to treat AEs that do not respond to other management outlined in the Treatment Manual.

All psychoactive medications, herbal supplements, non-prescription medications, and prescription medications must be reviewed by the Medical Monitor. Failure to comply with protocol requirements for concomitant medications may result in withdrawal from treatment, depending on the investigator and Medical Monitor judgment.

6.8.2.1 Acutely Prescribed Medications

Acutely prescribed medication may be considered necessary if the participant experiences severe, persisting emotional distress, anxiety, or insomnia that is not resolved via empathetic listening or

diaphragmatic breathing. The study site will supply acutely prescribed medication that will be obtained locally if prescribed by the site physician.

The name, dosage regimen, and date of the acutely prescribed medication administered will be recorded.

Although the use of acutely prescribed medications is allowable at any time during the study, the use should be delayed, if possible. The site physician and therapist should use their clinical judgement as to if/when it is clinically appropriate to intervene pharmacologically.

6.8.3 Prohibited Medications

To be enrolled in the study participants must:

- Be willing to comply with all medication requirements per protocol. Medications will only be discontinued after enrollment per clinical judgment of the site physician in consultation with the prescribing physician.

The research team should only approve medications that clearly would not be expected to have any interactions with MDMA.

7.0 Discontinuation of Study Intervention and Participant Discontinuation/Withdrawal

Discontinuation of the site or study as a whole is detailed in [Appendix 1: Regulatory, Ethical, and Study Oversight Considerations](#).

7.1 Discontinuation of Study Intervention

In rare instances, it may be necessary for a participant to permanently discontinue study intervention. If study intervention is permanently discontinued, the participant may remain in the study and continue with remaining individual sessions, but will not participate in any further group therapy sessions. If the investigator determines it is in the participant's best interest to completely withdraw from the study, an early discontinuation visit should be conducted..

7.2 Participant Discontinuation/Withdrawal from the Study

- A participant may withdraw from the study at any time at their own request or may be withdrawn at any time at the discretion of the investigator for safety, behavioral, or compliance reasons. This is expected to be uncommon.
- At the time of discontinuing from the study, if possible, an early discontinuation visit should be conducted..
- The participant will be permanently discontinued from the study intervention and the study at that time. The site team will provide the participant with a plan moving forward as described in [Section 8.4.4 Plan Moving Forward](#).
- If a participant develops any Exclusion Criteria that, in the opinion of the Medical Monitor or Site, affects the safety of the participant, the participant will discontinue treatment in Experimental Sessions but may remain in the study for any individual associated non-drug Therapy and Integrative Sessions.
- If a participant withdraws consent for disclosure of future information, the sponsor may retain and continue to use any data collected before such a withdrawal of consent.

- If a participant withdraws from the study, they may request destruction of any samples taken and not tested, and the investigator must document this in the site study records.
- If a participant withdraws, cohort will continue with reduced size.

7.3 Lost to Follow-up

A participant will be considered lost to follow-up if they repeatedly fail to return for scheduled visits and is unable to be contacted by the study site.

The following actions must be taken if a participant fails to return to the clinic for a required study visit:

- The site must attempt to contact the participant and reschedule the missed visit as soon as possible, counsel the participant on the importance of maintaining the assigned visit schedule and ascertain whether the participant wishes to and/or should continue in the study.
- Before a participant is deemed lost to follow-up, the investigator or designee must make every effort to regain contact with the participant (e.g., 3 telephone calls or emails). In addition, site shall reach out to the contact person (relative, spouse, close friend, or other support person) provided by the participant. Finally, if necessary, a certified letter to the participant's last known mailing address or local equivalent methods. These contact attempts should be documented in the participant's medical record.
- Should the participant continue to be unreachable, they will be considered to have withdrawn from the study.

8.0 Study Assessments and Procedures

- Protocol waivers or exemptions are not allowed.
- Immediate safety concerns should be discussed with the sponsor immediately upon occurrence or awareness to determine if the participant should continue or discontinue study intervention.
- Adherence to the study design requirements, including those specified in SoA, is essential and required for study conduct.
- All screening evaluations must be completed and reviewed to confirm that potential participants meet all eligibility criteria. The investigator will maintain a screening log to record details of all participants screened and to confirm eligibility or record reasons for screening failure, as applicable.
- Procedures conducted as part of the participant's routine clinical management (e.g., blood count) and obtained before signing of the ICF may be utilized for screening or baseline purposes provided the procedures met the protocol-specified criteria and were performed within the timeframe defined in SoA.
- The Clinical Research Associate (CRA) should be notified of any delays or deviations to study procedures and Medical Monitor consulted if necessary. If there are delays of more than 7 days between visits or contact, the site should assess the need for additional telephone contact with the participant to ensure safety.

8.1 Screening Period

Prospective participants may be pre-screened by telephone to ascertain if they meet basic eligibility criteria. Data from potential participants who do not pass telephone screening will not be entered in the eCRF, but reason of ineligibility will be documented on the Screening Log.

All individuals who are pre-screened should be assigned a Screening Number and recorded on the Screening Log.

At any time during Screening, if a potential participant is deemed ineligible, they will be classified as a Screen Failure, notified that they are not eligible for the study, and not be scheduled for any additional Screening assessments. Participants who are eligible by pre-screening will be invited to undergo the informed consent process, either in-person or via telemedicine as permitted by local and study site regulations.

Site staff (preferably a member of the therapy team who would be treating this potential participant) or central screener will explain and obtain written (or electronic) informed consent using the IRB-approved ICF. Written consent must be obtained prior to performing any tests or evaluations for the study. The signature may be obtained using an electronic 21 CFR Part 11 compliant system due to COVID-19. Discussion about the ICF may take place over a telemedicine visit or at the first in-person visit. If a participant fails Screening and is rescreened at a later date, a new copy of the ICF should be signed.

Screening may take place over multiple visits and will be completed in-person, via tele-assessment, or over the telephone. To allow for recruitment and scheduling of each group therapy cohort, there is flexibility in the timing window of the screening procedures permitted in the protocol, see [Section 5.5 Criteria for Temporarily Delaying](#).

Medical records, if available, should be requested from the participant’s general practitioner to ensure a comprehensive medical history has been obtained.

Table 4: Screening Period and Enrollment

Visit	Visit Description	Individual or Group	Visit Timing
Phone Screening	Phone calls	Individual	Prior to initial screening
Site Screening	In-person Visits & Labs	Individual	After Phone Screening
IR Screening	Initial IR Screening and Screening CAPS-5 (T0)	Individual	After initial eligibility met (may occur over 2 sessions)
Enrollment	Enrollment Review	Individual	~5 days (4 to 14 days) post IR Screening

8.1.1 Independent Rater Screening Assessment

If a participant meets initial eligibility during Screening, an IR will continue the eligibility assessment via tele-assessment after reviewing the results of the LEC-5 and SCID-5-SPQ. The IR interview may be recorded to assess reliability of ratings. If possible, the potential participant should be present at the study site during this assessment, in case the therapy team is needed for support. If a participant reports suicidal ideation during this assessment, the IR will contact the therapy team after the call and present any concerns. The therapy team will follow-up with the participant to ensure safety, provide support, recommend treatment, or schedule a visit to the study site.

- Using the results of the SCID-5-SPQ to guide the interview, the IR will perform the SCID-5-PD.
- The IR will also ask relevant questions from the DDIS to identify dissociative disorders and administer the Since Last Visit C-SSRS to determine suicidal risk.

- The IR will complete MINI interview.
- The IR will measure the CAPS-5 at screening (referred to as Screening CAPS-5 T0) to assess eligibility criteria.
- The IR screening may take place over 2 sessions.

The results from the CAPS-5, MINI, SCID-5-PD, DDIS, and C-SSRS will be provided to the therapy team at the site to review along with all other Screening information to determine eligibility. Items assessed by the IR at this visit will be confirmed in the Preparatory Period by clinical observation. If site staff deem the participant eligible, schedule Enrollment (Visit 0).

After the initial screening visits, the IRs will be blinded to visit number, number of treatments received and any study data for the participant. IR visits will be assigned based on availability.

8.1.2 Enrollment

In advance of Enrollment, the site team will review all notes from Screening visits, medical assessments, IR assessments, notes, discussions, medical records, and measures against eligibility criteria. If the participant is eligible, the participant will be notified of enrollment in person or via telephone/tele-assessment.

8.1.2.1 Enrollment Review

The site team will review the results of the IR visit to ensure that the participant continues to meet eligibility criteria, prior to CAPS-5 assessment, consulting with the Medical Monitor as required.

At Enrollment, the site team will confirm eligibility by reassessing specified eligibility criteria and ensuring that the participant continues to agree to all lifestyle modifications. If >3 weeks elapse from Enrollment Review (Enrollment) and the start of group therapy (Preparatory Session 1), confirm no clinically significant changes in health.

8.2 Preparatory Period

Medication tapering will be initiated following enrollment, in collaboration with the prescribing physician, as applicable. Participants will undergo four Preparatory Sessions lasting approximately 90 minutes with the therapy team prior to the first Experimental Session. Adherence criteria for Preparatory Sessions should be followed per the Treatment Manual. The Preparatory Period will last 3-4 weeks, depending on duration of medication tapering. There must be at least 48 hours between Preparatory Sessions. The minimum time to complete the Preparatory Period is 3 weeks. In these visits, the therapy team will work with the participant to prepare for MDMA-assisted therapy, begin building therapeutic alliance, and promote a safe set and setting for confronting trauma-related memories, emotions, and thoughts.

Table 5: Preparatory Sessions

Visit	Individual or Group	Visit Timing
Preparatory Session 1	Group	~1 week (3 to 14 days) after Enrollment
Preparatory Session 2	Group	~1 week (3 to 14 days) after Preparatory Session 1
Preparatory Session 3	Individual	After Preparatory Session 1, but before (Baseline); Preparatory Session 2 and Preparatory Session 3 order may differ; post Taper
Baseline CAPS-5 (T1)	Individual	After Preparatory Session 3, but before Preparatory Session 4
Preparatory Session 4	Group	~3 weeks (17 to 28 days) after Preparatory Session 1; 1 to 14 days before Experimental Session 1

8.2.1 Group Preparatory Sessions 1, 2, and 5

Group Preparatory Sessions during the Preparatory Period will focus on psychoeducation about PTSD, building safety for the therapeutic relationship, developing the therapeutic alliance, and preparing participants for the first Experimental Session. Telephone calls may be scheduled between visits if indicated for tapering, safety, or any further questions about medical history.

At each 90-minute Preparatory Session, the therapy team or other qualified site staff will:

- Inquire about any possible changes in health to ensure the participant continues to meet all eligibility requirements. Record AEs as described in [Section 8.7: Adverse Events, Serious Adverse Events, and Other Safety Reporting](#).
- Inquire about concomitant medication use and adherence.
- Confirm that medication tapering is ongoing or complete, as appropriate.
- If medication tapering is ongoing at Preparatory Session 2, site team to schedule a phone call after tapering and stabilization are complete.
- Administer Since Last Visit C-SSRS to determine suicidal risk.
- Discuss goals and expectations for the Experimental Session, following standard procedures and techniques described in the Treatment Manual.

At any time during the Preparatory Period, if a potential participant is deemed to be ineligible, the site team will classify them as an Enrollment Confirmation Failure, notify the potential participant that they are unfortunately not eligible for the study, and not schedule additional assessments.

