Assess incidence of AESIs, defined as AEs specified in the protocol related to cardiac function, suicidality, and abuse liability.	All visits following enrollment	AEs reported in eCRF
Assess incidence of SAEs.	All visits	SAEs reported in eCRF
Assess incidence of psychiatric concomitant medications taken.	Phone and Site Screening, all visits with exception of Preparatory Session 1 and (Outcome)	Medication review
Assess relative incidence of positive or serious ideation and suicidal behavior.	All site visits	C-SSRS
Assess mean changes in physiological measures.	Site Screening, Experimental Session 1 and Experimental Session 2 (pre-IMP administration and end of visit)	Blood pressure, heart rate, and body temperature
Exploratory		
Evaluate group cohesion within and between cohorts based on comparison of PTSD treatment outcome.	CAPS-5 (Baseline) and (Outcome)	CAPS-5
Assess changes in severity of dissociative symptoms associated with PTSD.	DSP-1 (Baseline (Outcome)	DSP-I
Evaluate the effect of adverse childhood experiences on PTSD treatment outcome as a covariate.	Preparatory Session 3 & Safety review, (Baseline), and (Outcome)	ACE CAPS-5
Characterization of PTSD severity with a descriptive time course plot.	Preparatory Session 3 & Safety review, , Integrative Session 1.4, and (Outcome)	PCL-5

Objectives	Assessment Window	Endpoints
Assess changes in severity of dissociative symptoms associated with PTSD treatment outcome.	CAPS-5 T1 (Baseline) and CAPS-5 T2 (Outcome)	DSP-I
Assess changes in group cohesion.	Preparatory Session 3 & Safety review, Integrative Session 1.4, Integrative Session 2.4, and Study Termination	GQ
Assess changes in depression symptoms.	Preparatory Session 3 & Safety review and Study Termination	BDI-II
Assess changes in attachment dynamics.	Preparatory Session 3 & Safety review and Study Termination	ECR-S
Assess changes in positive outcomes following trauma.	Preparatory Session 3 & Safety review and Study Termination	PTGI
Assess changes in perceived social support.	Preparatory Session 3 & Safety review and Study Termination	SPS
Assess changes in self-compassion.	Preparatory Session 3 & Safety review and Study Termination	SCS
Assess changes in health economics.	Preparatory Session 3 & Safety review and Study Termination	CSI
Assess changes in quality of life.	Preparatory Session 3 & Safety review and Study Termination	EQ-5D-5L
Assess changes in workplace productivity.	Preparatory Session 3 & Safety review and Study Termination	HPQSF

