Suicide and Risk of Self-Harm	Suicidal ideation and behavior are disease related events with high incidence in populations of people with PTSD, especially those suffering from chronic PTSD. Due to the nature of the therapeutic method, wherein a person may re-experience emotions associated with the traumatic event in order to reprocess the memory in a new, therapeutic way, thoughts of ending one’s life may surface during the process. In previous MAPS-sponsored clinical trials C-SSRS scores have escalated during the Preparatory Sessions,	
 • Should a participant be at serious risk to themselves, then the therapy team and site staff will intervene appropriately, consistent with professional practice standards. In extreme circumstances, this may involve summoning external crisis management teams for further assessment which may lead to involuntary hospitalization.

	
which is thought to be a result of preparatory discussion of traumatic experiences, and/or participants concomitant tapering off long-prescribed medications, such as SSRIs and benzodiazepines.
 
During both non-drug and MDMA-assisted therapy sessions, participants are asked to think about and discuss their experiences, thoughts, and emotions related to their condition. Participants are also asked to report on their suicidality in these sessions and every other day over phone through C-SSRS administration. They may experience intense emotional responses to recalling and speaking about this material. As MDMA is only administered in combination with therapy, the distress associated with therapy is unavoidable and is considered a necessary part of the therapeutic process that requires proper facilitation and support from therapists.
	

Inadequate pain management in participants using non-approved opioids
	
Certain long-acting opioid pain medications are not permitted during the study due to the potential QT-prolonging effects. The permitted opioid medications allowed in the study are listed in Section 6.8.2 Permitted Concomitant Medications. For some participants, the ability to achieve acceptable pain relief from the new opioid may not be possible.
	
 • Participants requiring opioid pain medication may be cross-tapered to an approved opioid medication with an acceptable QT-prolongation profile.

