6.8.1 Psychiatric Medications

Psychiatric medications approved for treatment of PTSD, are under investigation for treatment of PTSD, or which are used off-label to treat symptoms of PTSD are not permitted during the trial and must be tapered during the Preparatory Period. If the participant is being treated with any such medication(s) at enrollment, the participant will be encouraged to discuss medication tapering with their outside treating physician and will be required to give the site physician permission to do so as well. The medications will then be tapered in an appropriate fashion to avoid withdrawal effects and discontinued at least five half-lives plus one additional week for stabilization before Baseline to avoid the possibility of any interaction.

The site physician will consult the prescribing physician to initiate medication tapering for participants, as they must refrain from taking psychiatric medications throughout the study, with some exceptions, see [Section 6.8.2 Permitted Concomitant Medications](#). The prescribing physician's opinion about medication discontinuation should be documented in the participant's study record. Tapering will follow a time course appropriate for the medication based on its half-life, with Baseline scheduled to occur after complete washout (five half-lives plus at least 1 week for stabilization). If the health of the participant worsens after tapering, the participant will be withdrawn from the study and will be treated according to standard clinical practice. This will be recorded in the eCRF.

The therapy team will request information about any changes in medication at each contact. The site physician will be responsible for reviewing and confirming all medications collected during the study.

All medications, non-prescription and prescription, will be collected from Screening through 7 days after the last Experimental Session. From 7 days after the last Experimental Session through Study Termination, only prescription or non-prescription medications taken to treat AEs will be collected. Throughout the protocol, all medications used to treat AEs will be collected, and all changes including discontinuations or additions to medications will be collected. The study team will inquire and document all information about withdrawal and tapering of medications, concomitant medication, and medication adherence in the eCRF Concomitant Medications.

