8.2.2 Individual Preparatory Session 3 and Safety Review

At Preparatory Session 3 and Safety Review, the site team will confirm the participant continues to be eligible for the study by reassessing specified safety criteria and ensuring that the participant continues to agree to all lifestyle modifications. This may require approval from the Medical Monitor for the initial participants until confidence is established. If any eligibility requirements are not met before or during Preparatory Session 3 and Safety Review, the participant will be considered a Pre-Dosing Early Termination.

For eligible participants at Preparatory Session 3 and Safety Review, the therapy team or other qualified site staff will:

- Complete the third 90-minute Preparatory Session with the purpose of confirming all enrollment is met and completing final preparation for the first Experimental Session.
- Inquire about any possible changes in health to ensure the participant continues to meet all eligibility requirements. Record AEs as described in [Section 8.7: Adverse Events, Serious Adverse Events, and Other Safety Reporting](#).
- Inquire about concomitant medication use and adherence.
- Administer Since Last Visit C-SSRS to determine suicidal risk.
- Perform urine pregnancy test (for PAPB only).
- Perform urine drug test.
- Actively support participant in the completion of Baseline self-reported measures. Completion of measures does not need to be recorded.

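### Self-report baselines are taken at Preparatory Session 3, after taper but possibly before washout is complete, while the CAPS-5, SDS and DSP-I baselines wait for washout

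*Protocol*

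**What the plan says.** Section 6.8.1 requires psychiatric medication for PTSD to be tapered in the Preparatory Period, "with Baseline scheduled to occur after complete washout (five half-lives plus at least 1 week for stabilization"). Section 8.2.3 identifies Baseline as the independent-rater visit at which CAPS-5 (T1), SDS and DSP-I are administered. Table 5 in Section 8.2 places that visit "After Preparatory Session 3, but before Preparatory Session 4".

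The questionnaires follow a different path. Under Section 8.2.2, site staff at Preparatory Session 3 are to "Actively support participant in the completion of Baseline self-reported measures". The Objectives and Endpoints table in the Synopsis gives the window for change in BDI-II, ECR-S, PTGI, SPS, SCS, CSI, EQ-5D-5L and HPQSF as "Preparatory Session 3 & Safety review and Study Termination". Session 3 is also the first time point for the GQ and for the PCL-5, whose stated use is "Characterization of PTSD severity with a descriptive time course plot".

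The drug condition on Session 3 is the last phrase of its Table 5 entry: "Preparatory Session 2 and Preparatory Session 3 order may differ; post Taper". Section 8.2.1 treats the end of tapering and the end of stabilization as two things: if tapering is still under way at Preparatory Session 2, the "site team to schedule a phone call after tapering and stabilization are complete".

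**The concern.** The protocol evidently regards the period after the last dose as unsuitable for measuring baseline severity, since it makes the rater visit wait for drug clearance and a further week. The self-reports have no such protection, although they too serve as the pre-treatment value for change scores.

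Table 1 in Section 2.3.1 reports that C-SSRS scores rose during Preparatory Sessions in earlier trials. It attributes this to discussion of trauma, to "participants concomitant tapering off long-prescribed medications, such as SSRIs and benzodiazepines", or to both. The later values come from a different drug state: Section 8.4.1 keeps the medication rules in force until after Study Termination, well beyond any washout.

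The study has one arm, so no comparator cancels a temporary disturbance at the first measurement. The self-report results would also rest on a different drug state from the CAPS-5 results they are likely to be read beside.

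**Working it through.** **1. Which visit is protected.** Section 6.8.1 ties washout to Baseline. Section 8.2.3 makes Baseline the rater visit. Table 5 puts the rater visit after Session 3. No text at hand ties Session 3 to washout.

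**2. How far Session 3 can precede T1.** Count days from Preparatory Session 1, using the Table 5 windows and the 48-hour minimum spacing in Section 8.2.
- Earliest Session 3: day 2.
- Latest Session 4: day 28, so latest T1 (before Session 4, in whole days): day 27.
- Largest gap: 27 − 2 = 25 days.

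Session 1 is 3 to 14 days after Enrollment. At this gap, Session 3 falls between day 3 + 2 = 5 and day 14 + 2 = 16 after Enrollment, and T1 between day 3 + 27 = 30 and day 14 + 27 = 41. A longer taper shortens the gap without closing it: T1 must wait for washout, while Session 3 may fall anywhere between the end of taper and T1.

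**3. Whether washout fits in the gap.** Washout W = 5 × t + 7 days, where t is the half-life. The protocol lists no half-lives, so the values of t are assumptions.

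| t (days, assumed) | W (days) | Last dose just before Session 3 permitted? |
|---|---|---|
| 1 | 5 × 1 + 7 = 12 | yes |
| 2 | 5 × 2 + 7 = 17 | yes |
| 3 | 5 × 3 + 7 = 22 | yes |
| 4 | 5 × 4 + 7 = 27 | no, exceeds 25 |

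The limit is t = (25 − 7) / 5 = 3.6 days. Up to that half-life, a participant can take the last dose just before Session 3, complete the questionnaires at once, and still meet the T1 rule. At t = 4, Session 3 must come at least 27 − 25 = 2 days after the last dose, which is still early in a 27-day washout.

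**4. What this does to the estimate.** Section 9.3.3 analyses exploratory outcomes like the primary, as change from baseline adjusted for baseline. In a single arm, the fitted change at the mean baseline equals the raw mean change, so the adjustment does not remove a baseline shift. If a share s of participants has a temporary shift w at Session 3, the mean change moves by s × w.

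The protocol gives neither s nor w. Purely as assumptions, s from 1/6 to 2/3 and w from 2 to 8 scale points give 1/6 × 2 = 0.3 up to 2/3 × 8 = 5.3 points. On a scale where higher is worse, a withdrawal effect (w positive) overstates improvement and masking by residual drug (w negative) understates it.

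**5. Which scales are exposed.** The EQ-5D-5L asks about health on the day of completion (Section 8.5.4.10). The BDI-II and PCL-5 measure current symptom severity. The CSI as modified here has a 6-month recall (8.5.4.7) and the HPQSF uses questions over 4 weeks (8.5.4.11). The ACE records childhood events. The GQ, ECR-S, PTGI and SPS measure group relationships, attachment, growth and social support. These are little exposed or not obviously so.

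**The case against.** The strongest reply is that Section 8.2.2 itself labels the Session 3 questionnaires as baseline measures, so a site could apply the Section 6.8.1 rule to them. That reading is possible, but Table 5 gives Session 3 a looser condition and puts it before Baseline. The label makes the text ambiguous; it does not settle it. The Schedule of Activities to which the protocol refers is not in the text available and may hold a tighter rule. If so, Table 5 still needs to agree with it.

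Two safeguards count. Section 6.8.1 says the taper is to be done so as to avoid withdrawal effects, and it withdraws participants whose health worsens after tapering. Both reduce the exposure; neither removes milder shifts. Section 8.5.4.4 also describes the BDI-II as not unduly sensitive to daily mood variation, though a washout of one to several weeks is longer than that.

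A reader might infer that improvement is certain to be inflated. The document does not support that: Table 1 concerns the C-SSRS, names trauma discussion as an alternative or joint cause, and does not exclude masking by residual drug. Trauma discussion could also raise scores at T1, so it does not separate the two baselines. A reader might also infer that every self-report scale is affected, or that questionnaires the day after the last dose are possible for any drug. Steps 3 and 5 show otherwise.

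Consequences are limited. Section 9.1 plans no formal hypothesis testing, Section 9.5 describes a feasibility study without a power target, and the PCL-5 feeds only a descriptive plot.

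**Conclusion.** The point holds as an inconsistency between two baselines. In participants who taper, the BDI-II, the EQ-5D-5L and the first PCL-5 point can be measured during washout, up to 25 days before T1, without breaching any visible rule. The resulting bias in mean change is possible rather than certain. Overstatement is plausible from the protocol's own risk table, but the direction is not established. The 0.3 to 5.3 point range rests wholly on assumed inputs and is not an estimate for this trial.

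CAPS-5, SDS and DSP-I are taken at T1 after washout and are untouched. The conclusion assumes that the unseen Schedule of Activities does not already require Session 3 to follow washout. The matter is worth correcting because the remedy is cheap, but it concerns exploratory outcomes only.

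**What to change.** Have the baseline self-reports completed on the day of the Baseline CAPS-5 (T1), before Preparatory Session 4, with site staff support as Section 8.2.2 now provides. Reconcile Table 5, Section 6.8.1 and Section 8.2.2 accordingly, and change the assessment windows in the Synopsis for the measures that start at Session 3. Preparatory Session 3, the taper and the Safety Review stay as they are.

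This adds no visit and no assessment. The cost is a longer T1 day and the need to arrange site support for questionnaires around a rater visit held by tele-assessment.
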